7.2.7. Physical Examination

Complete Physical Examination

The following parameters and body systems will be examined and any abnormalities described: General appearance, weight and height, skin (presence of rash), HEENT (head, eyes, ears, nose and throat), lungs (auscultation), heart (auscultation for presence of murmurs, gallops, rubs), lower extremities (peripheral edema), abdominal (palpation and auscultation), neurologic (mental status, station, gait, reflexes, motor and sensory function, coordination) and lymph nodes. For children under 40 kg, body weight obtained at study visits will be used to adjust dosing as the child grows.

Applicable to Investigative Sites in the UK and Belgium: a full skin cancer examination must be performed as part of the complete physical examination.

Targeted Examination

An abbreviated physical examination will be performed assessing the following: examination of skin, heart, lungs, lower extremities for peripheral edema, abdomen and lymph nodes, weight and height. Any clinically significant changes from the baseline examination should be recorded as AEs.

Applicable for subjects enrolled from A3921165:

If rash is present, the type of rash should be noted (e.g., typical sJIA rash, varicella rash, herpes zoster lesions, or other types of rash). The parent/guardian/subject should perform at least weekly skin checks between visits and any concern for potential chickenpox or shingles be reported to the investigator immediately. Please refer to [Appendix 16](#).

7.2.8. Assessment of Pubertal Development

Determination of physical and sexual maturation will be performed annually at study visits using the Tanner stages by a trained physician/clinician in the presence of a parent/legal guardian or clinic staff member, until the subject has reached Tanner Stage 5.

In the event the parent/legal guardian or child 9 years or older refuses the examination for sexual maturity, or if not possible per site practice or local regulations, subject self-assessment of Tanner staging that uses photographs or line drawings corresponding to the Tanner stages will be offered to obtain information on pubertal status while avoiding intrusiveness.

Based on a multi-informant investigation, Dorn et al. (1990)⁹ and Taylor et al. (2001)¹⁰ found that when boys and girls were shown schematic drawings (5 ordinal-scaled drawings/photographs corresponding to the Tanner stages), their self-ratings correlated quite well with health-care-provider examination Tanner staging.

The Tanner stage rating will be assigned by the clinician/physician based on the exam or based on the subject self-report. If the clinician believes the subject's self-report may reflect an earlier or later pubertal stage than the clinician believes is correct, the clinician will review

the self-report form with the subject and/or parent/legal guardian to clarify the subject's responses. This review will be done in the presence of another person, either the parent/legal guardian or a clinic staff member. At the end of the review, the clinician will then assign a best estimate Tanner stage rating.

Note that pubertal development in the U.S. begins as early as age 8 and completes as late as age 17. Once a subject has reached the highest stage of development (Stage 5) then that score may be carried forward for the remainder of the study.

7.2.9. Laboratory Tests

Blood and urine samples will be collected at the time points identified in [Schedule of Activities](#) and [Section 6](#) the protocol. Unscheduled clinical labs may be obtained at any time during the study to assess any perceived safety concerns.

Protocol required testing includes hematology (CBC with differential), urinalysis, chemistry panel (sodium, potassium, chloride, bicarbonate, calcium, glucose, urea nitrogen, creatinine, creatine kinase, total protein, total bilirubin, direct and indirect bilirubin, alkaline phosphatase, gamma-glutamyl transferase, albumin, aspartate aminotransferase, alanine aminotransferase, and urine pregnancy testing (females of childbearing potential only).

Lipid Panel (cholesterol, indirect LDL, direct HDL, apolipoproteins A-1 and B, triglycerides) will be collected under fasting conditions, if possible, at the baseline visit for subjects who roll over more than 14 days after their EOS Visit from their qualifying/index study, every 6 months through year 5 and then every 12 months after year 5, and at the End of Study/Early Termination Visit for all subjects who enroll in this study.

Hepatitis B, Hepatitis C virus antibody (HCV Ab), and HIV-1/HIV-2 antibody screen will be obtained at the screening visit for subjects who enroll more than 14 days after their EOS Visit from their qualifying/index study.

In case of insufficient sample or issue on the sample quality (eg, hemolysis or clotting) the subject should return within 1 week to collect a new sample.

Creatinine clearance will be evaluated at every study visit using the Modified Schwartz equation or Cockcroft-Gault equation. ([Appendix 5](#))

Hepatitis B testing:

The blood sample will first be analyzed for HBsAg and HBcAb. If HBsAg is positive, the subject is excluded from the study. If the sample is HBsAg negative but HBcAb positive, the subject will be tested for HBsAb. If when tested, the HBsAb test is negative, the subject will be excluded from the study. Hepatitis B testing will not be performed in subjects determined to be HBs Ab positive in their qualifying study.

Hepatitis C testing:

HCV RNA is tested in case a positive HCV Ab result is obtained. Only subjects with negative HCV Ab or HCV RNA will be allowed to enroll in the study. To conserve blood volume at screening, HCV RNA sample collection may be deferred and collected only if required to confirm eligibility based on the HCV Ab results.

Subjects who are receiving concomitant MTX, leflunomide, sulfasalazine, chloroquine, or hydroxychloroquine should have Hematology (CBC with differential) and chemistry laboratory tests (eg, electrolytes, BUN, creatinine, liver function tests, etc.) obtained as appropriate for standard of care.

Tuberculosis testing

QuantiFERON®-TB Gold or Gold Plus In-Tube will be obtained at the screening visit for subjects who enroll more than 14 days after their EOS Visit from their qualifying/index study. Annual TB testing will be performed using the QuantiFERON®-TB Gold or Gold Plus In-Tube test. Subjects should withhold study medication on the day of the visit to limit the number of potential false positive results.

The following Table 3 lists the components of all laboratory testing (mandatory and optional) that will be conducted during the course of this study.

Table 3. Laboratory Testing

Laboratory Testing Profile	Tests Included
Infections	QuantiFERON®-TB Gold or Gold Plus In-Tube test, hepatitis C virus antibody (and hepatitis C virus RNA if needed), hepatitis B surface antigen and hepatitis B core antibody (and hepatitis B surface antibody if needed), HIV-1/HIV-2 antibody screen.
Hematology	Hemoglobin, hematocrit, RBC, WBC, neutrophils (%), abs), lymphocytes (%), abs), Monocytes (%), abs), eosinophils (%), abs), basophils (%), abs), platelets.
Chemistry Panel	Urea nitrogen, creatinine, glucose, calcium, sodium, potassium, bicarbonate, chloride, total protein, total bilirubin, direct bilirubin, indirect bilirubin, alanine aminotransferase (ALT), aspartate aminotransferase (AST), alkaline phosphatase, gamma-glutamyl transferase (GGT), albumin, creatine kinase (CK).
Lipid Panel (fasting, if possible)	Total cholesterol, direct HDL, indirect LDL, apolipoprotein A-1 and B, triglycerides.
Urine	Specific gravity, pH, protein, glucose, ketones, blood and leukocyte esterase, urine microscopy. ^a Urine HCG pregnancy testing for women of childbearing potential.
Acute Phase Reactants	C-reactive protein (CRP), erythrocyte sedimentation rate (ESR).
Macrophage activation syndrome (MAS) ^b	Ferritin, fibrinogen, platelets, triglycerides.

Table 3. Laboratory Testing

Laboratory Testing Profile	Tests Included
a. Only if dipstick positive for blood or protein or clinically indicated.	
b. MAS diagnostic laboratory testing (sJIA subjects only): if MAS is suspected in a febrile subject, a blood sample will be collected to assess Ferritin and Fibrinogen serum levels in order to confirm the diagnosis of MAS. Platelet and triglyceride levels from the standard hematology and lipid evaluations will also be reviewed for confirmation of a MAS diagnosis.	

Clinically significant abnormal findings should be recorded as AEs if they meet any of the following criteria:

- Test result is associated with accompanying symptom; and/or
- Test result requires additional diagnostic testing or medical/surgical intervention; and/or
- Test result leads to a change in study dosing or discontinuation from the study, significant additional concomitant drug treatment, or other therapy; and/or
- Test result is considered to be an adverse event by the Investigator or sponsor.

Abnormal test results determined to be caused from laboratory error should not be reported as AEs. Clinically significant laboratory findings at the final assessment should be followed to resolution or until determined by the Investigator to be stabilized. Repeat tests may be indicated to establish this. Refer to [Appendix 8](#) for laboratory discontinuation criteria.

7.2.9.1. Blood Volume

Every effort will made to minimize the number of blood sampling and volumes collected. Low volume pediatric tubes will be used where possible. Maximum blood volume during the first year of the study will be approximately 90 mL. After the first year of participation, annual blood volume will be approximately 30 mL. The total volume taken during the study does not exceed 2.4 mL/kg during any period of 30 consecutive days.

7.2.10. Risk Factor Check for Venous Thromboembolism

All subjects will undergo a risk factor check at each study visit to check for newly developed risk factors for venous thromboembolism.²⁶ This information is to be captured in the subject's source file and on the relevant case report form.

A subject may be at high risk for venous thromboembolism if he/she:

- has heart failure or prior myocardial infarction within the past 3 months;
- has inherited coagulation disorders;

- has had venous thromboembolism, either deep venous thrombosis or pulmonary embolism;
- is taking combined hormonal contraceptives or hormone replacement therapy;
- has malignancy (association is strongest with cancers other than non melanoma skin cancers);
- is undergoing major surgery or is immobilized.

Additional risk factors for venous thromboembolism, such as age, diabetes, obesity (BMI>30), smoking status, hypertension, and first degree family history of VTE should also be taken into consideration by the investigator and the Sponsor medical monitor when evaluating the benefit:risk for each individual subject whether to modify their dose of tofacitinib.

If a subject has 1 or more of the risk factors for venous thromboembolism listed above, investigator judgement based on Exclusion Criterion 25 will apply to determine whether the subject is appropriate for entry into this study.

If a subject has 1 or more of the risk factors for venous thromboembolism listed above under Amendment 10 and is receiving tofacitinib 5 mg BID, they may remain on tofacitinib 5 mg BID after careful investigator assessment of benefit:risk.

For subjects who do not have any of the risk factors for venous thromboembolism listed above under Amendment 10, he/she will remain on their assigned tofacitinib dose.

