5.2.1. Tofacitinib Temporary Withholding

Dosage of tofacitinib may be temporarily discontinued for up to 28 consecutive days, for more severe cytopenias, for infections which do not meet criteria for serious infections (those requiring parenteral antimicrobial therapy or hospitalization), for surgical procedures or other moderately severe AEs. Additionally, tofacitinib must be temporarily discontinued for a minimum of 6 weeks prior to giving live or live-attenuated vaccines. Tofacitinib would then be restarted a minimum of 6 weeks after receiving the vaccine. Withholding of study drug is not necessary when administering non-live vaccines, including inactivated influenza vaccine and non-live COVID-19 vaccines.

Per Amendment 10, for subjects with suspected venous thromboembolism, treatment with tofacitinib should be temporarily withheld while the subject is evaluated. If venous thromboembolism is confirmed, discontinue treatment with tofacitinib and withdraw the subject from the study (see [Section 6.2.6: Subject Withdrawal](#)).

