- Two sequential increases in serum creatinine >50% over the average of screening and baseline values (as defined above) OR an absolute increase in serum creatinine \geq 0.5mg/dL ($\geq 44.2 \mu\text{mol/L}$) over the average of screening and baseline values (as defined above)

AND

A confirmed (two sequential) CrCl decrease of >30% over the average of screening and baseline values (as defined above).

(N.B. Screening and baseline values to be used for this discontinuation criteria are defined at the beginning of [Appendix 8](#))

If the serum creatinine increase and the CrCl decrease have an identifiable and reversible cause (e.g. concomitant medication), then an additional retest may be considered after discussion with Sponsor study clinician or medical monitor. After retest, a decision for the subject to continue in the study will be made with the Sponsor study clinician or medical monitor.

- Other serious or severe AEs, after consultation with the Pfizer Medical Monitor. For example, subjects with a malignancy (exception of adequately treated or excised non-metastatic basal cell or squamous cell cancer of the skin or cervical carcinoma in situ) must be discontinued from the study. All malignancy events should be reported as serious AEs.

¹ In each case, there is a need for additional investigations, such as review of ethanol, recreational drug and dietary supplement consumption; testing for acute hepatitis A, B or C infection and biliary tract imaging should be promptly discussed with the Pfizer Medical Monitor.

Appendix 9. Evaluation Of Potentially Malignant Tumors, Suspicious Lymphadenopathy, Possible Extra-Nodal Lymphoproliferative Disorder (LPD)

The following steps should be taken in the event of potentially malignant tumors, suspicious lymphadenopathy or possible extra-nodal lymphoproliferative disorder (LPD) which might arise in the course of this study.

When there is a decision to biopsy a potentially malignant tumor, lymph node, or other tissue, the investigator and/or consultants should contact the Pfizer study team to discuss the issue and any decisions as soon as possible. It is recommended that specialists with experience in the evaluation of immunosuppressed subjects be consulted.

If a biopsy for lymphadenopathy or lymphoma is to be performed, the investigator or consultant should refer to the instructional slide deck in the Lymph Node Biopsy kit and review the following points with the surgeon and pathologist:

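### Section 7.2.10 lets a subject with VTE or malignancy remain on 5 mg BID at the investigator's judgement, while other protocol passages require discontinuation

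*Protocol*

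**What the plan says.** Protocol Section 7.2.10 opens with the scope of the check: "All subjects will undergo a risk factor check at each study visit to check for newly developed risk factors for venous thromboembolism". Six high-risk factors follow. Two of them are "has had venous thromboembolism, either deep venous thrombosis or pulmonary embolism" and "has malignancy (association is strongest with cancers other than non melanoma skin cancers". After the list, one sentence deals with entry and refers to Exclusion Criterion 25. The next deals with subjects who have a listed factor and are receiving 5 mg BID: "they may remain on tofacitinib 5 mg BID after careful investigator assessment of benefit:risk". A last sentence keeps subjects without any listed factor on their assigned dose.

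Section 5.2.1 says of VTE: "If venous thromboembolism is confirmed, discontinue treatment with tofacitinib and withdraw the subject from the study". Section 6.2.6 repeats this rule and refers to Appendix 8, which states it again.

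Appendix 8 also deals with malignancy, in the list of reasons for stopping treatment and withdrawing the subject. The entry begins "Other serious or severe AEs, after consultation with the Pfizer Medical Monitor. For example, subjects with a malignancy". It then excepts adequately treated or excised non-metastatic basal or squamous cell skin cancer and cervical carcinoma in situ, and says that the remaining subjects "must be discontinued from the study. All malignancy events should be reported as serious AEs".

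**The concern.** A deep vein thrombosis, a pulmonary embolism or a cancer that arises on study is a newly developed item on the Section 7.2.10 list. Read as written, that section leaves continued dosing to the investigator, while the discontinuation passages leave no such choice for confirmed VTE and say that a subject with a non-excepted malignancy must stop.

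The visit procedures make the permissive text the one a site is likely to open. In the Schedule of Activities (footnote 16) and the visit lists of Sections 6.1 and 6.2, the risk-check entry points to Section 7.2.10 and not to Appendix 8. A child could therefore stay on drug after an event that other passages treat as a reason for withdrawal. Section 2.3.1 names VTE and malignancy among the tofacitinib safety concerns and presents the VTE discontinuation criteria as part of how risk is managed in this study.

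**Working it through.** No arithmetic applies. The check is to put one subject, receiving 5 mg BID, through both sets of instructions.

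| Event in a subject on 5 mg BID | Section 7.2.10 | Other passages | Result |
|---|---|---|---|
| New confirmed VTE | Listed; continuation permitted on judgement | Sections 5.2.1 and 6.2.6 and Appendix 8: stop and withdraw | Conflict, in three places |
| New malignancy outside the Appendix 8 exceptions | Listed; continuation permitted on judgement | Appendix 8: must be discontinued | Conflict, in one place |
| Excepted skin cancer or cervical carcinoma in situ | Listed; continuation permitted on judgement | Appendix 8 excepts it | No conflict |
| Any of the other four listed factors | Listed; continuation permitted on judgement | No mandatory discontinuation stated for the factor itself | No conflict |

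**The three-place count holds for VTE only.** Section 5.2.1 does not mention malignancy, and Section 6.2.6 reaches it only by pointing to Appendix 8.

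**Could the permission be meant only for history before entry?** For VTE this is possible. A past VTE is not a stand-alone exclusion and goes to judgement under Exclusion 25, so an enrolled subject could have one. But the check is described as one for newly developed factors, and entry has its own sentence. The permission is addressed to subjects already receiving drug and is not limited to history. For malignancy the history reading leaves very little: Exclusion 20 already bars past or present malignancy apart from the same skin and cervical exceptions.

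**Effect on the analysis.** SAP Section 6.6 counts each subject once per event type and stops exposure at the first event. Drug taken after a VTE cannot change the VTE rate, and likewise for malignancy. Two other quantities can move:
- The risk period for other event types runs to the last dose plus 28 days (or last contact, if earlier), so it lengthens if the subject continues.
- The rate of adverse events leading to discontinuation from study depends on whether the site withdrew the subject.

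**Dose wording.** The permission names 5 mg BID. Table 2 in Section 5.1 gives 2 to 4 mg BID below 40 kg. Sections 1.2.2 and 2.3.2 also use 5 mg BID as a name for the regimen across ages, so it is unclear whether the sentence includes the lower weight-based doses.

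**The case against.** The strongest reply is that a site can comply with both texts. Section 7.2.10 is permissive and covers a general list; the VTE rule is specific and mandatory. Leave to stay on a dose despite a risk factor need not cancel a withdrawal rule. Amendment 10 introduced the risk check and the VTE withdrawal rule together, which suggests that they were meant to work side by side. The malignancy rule is given as an example under a line that calls for consultation with the medical monitor. This reading is plausible, and it may be what was intended. But the protocol states no precedence, Section 7.2.10 carries no exception, and the malignancy line still says must.

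A reader might infer more than the documents support:
- **That children below 40 kg with a risk factor have no dose instruction.** Section 5.1 sets the dose by weight for every subject at each visit. Section 7.2.10 also has a dose-neutral sentence on evaluating whether to modify an individual's dose. Only the meaning of 5 mg BID is open.
- **That Exclusions 20 and 25 contradict each other for malignancy at entry.** Under Section 4.2 any one criterion excludes. Judgement under 25 does not waive 20.
- **That the SAP Section 6.1 summary of subjects meeting the discontinuation criteria depends on which section the site followed.** It counts who met Appendix 8, not what the site then did.
- **That about 340 subjects are affected.** That is the projected number checked. Those affected are the subjects with an on-study VTE or a non-excepted malignancy.

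**Conclusion.** The inconsistency stands. It is firm for confirmed VTE, where one section conflicts with three others. It is narrower for malignancy, where it rests on Appendix 8 alone, with exceptions and a line on consultation. Two of the six listed factors are involved. The documents give no expected number of such events, so the number of subjects cannot be sized; per subject, the difference is between continuing and stopping drug after a potentially serious event. The case for correcting it rests on patient safety. The effect on analysis is limited to exposure time for other event types and to the rate of events leading to discontinuation.

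This conclusion assumes that the permission is read as written, without an unstated rule that the specific passage prevails. It takes no position on which clinical instruction is right.

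**What to change.** Reconcile Section 7.2.10 with Sections 5.2.1 and 6.2.6 and Appendix 8, so that each event has one instruction:

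1. State in Section 7.2.10 whether the permission to remain on dose applies to VTE or malignancy that arises on study.
2. Cross-refer from that sentence to the passage that governs each event.
3. As a minor wording point, say whether 5 mg BID in that sentence includes the weight-based doses of Table 2.

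The sponsor's clinicians decide the content. The cost is a few sentences in a protocol amendment or clarification letter, with no new procedures and no new data.

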7.3. Pregnancy Testing

For female subjects of childbearing potential, a serum or urine pregnancy test, with a sensitivity of at least 25 mIU/mL for hCG, will be performed locally at Screening and Baseline Visits for subjects who roll over within 14 days or more than 14 days after their EOS Visit from their qualifying/index study, at all study visits and at the End of Study/Early Termination for all subjects. If preferred, urine and/or serum pregnancy test may be performed at any time using the local laboratory.

A negative pregnancy result is required before the subject may receive the tofacitinib.

Pregnancy tests will also be done whenever one menstrual cycle is missed during the treatment period (or when potential pregnancy is otherwise suspected) and at the end of the study to confirm the subject has not become pregnant during the study. Pregnancy tests may also be repeated if requested by institutional review boards (IRBs)/ethics committees (ECs) or if required by local regulations.

A positive urine pregnancy test will be confirmed by a blood (serum) pregnancy test performed either locally or by the central laboratory.

In the case of a positive confirmed pregnancy, the subject will be withdrawn from study medication and from the study.

